### **7.2 Statistical Analysis Plan**

We will enroll a total of 24 patients, twelve patients to each cohort consisting of distinct radiation and immunotherapy treatment plans. For each study cohort, treatment-related toxicity is defined in Table 3 above (in the column “Discontinue Treatment/Off-Study Criteria”. Therefore, any patient meeting this criteria will be deemed to have experienced an “unacceptable” toxicity for the purposes of the trial. For each study condition, we plan to enroll 12 patients in cohorts of size 6. All patients will be monitored for at least 4 months from the beginning of RT, before declaring the treatment acceptable for enrolling the next cohort of 6 patients.

Continuous monitoring using the method of Thall [20] will be employed for each study cohort of 12 patients in cohorts of size 6 where each patient is monitored for at least 4 months from the start of RT. We will stop the trial if we have reason to believe that the treatment-related toxicity rate is more than 30%. Using the following probability rule

$$\Pr(\text{rate of treatment-related toxicity 4 months from the start of RT} > 30\% \mid \text{data}) > 0.80.$$

If we determine there is more than a 80% chance that the treatment-related toxicity rate is more than 30%, we will stop the trial. We will assume a beta(0.6, 1.4) distribution for treatment-related toxicity as this prior provides a mean of 30% and a standard deviation of 26.5%. Thus the trial will be stopped if

$$[\# \text{ of patients with treatment-related toxicity 4 months from day 1 of the start of RT} / \# \text{ of patients evaluated}]$$

$$\geq 3/6, 6/12$$

Therefore, we will stop either study cohort if we observe 3 or more treatment-related toxicities in the first 6 patients, or if we observe 6 treatment related toxicities at any time while evaluating all 12 patients. We will suspend accrual while evaluating the first 6 patients to ensure none of

the stopping boundaries have been reached prior to enrolling the final 6 patients of each study cohort. The operating characteristics from this decision rule are shown in Table X and are based on 1000 simulations for each scenario.

Table X. Operating characteristics for toxicity monitoring rule

Treatment-related Toxicity 4 months after start of RX	Probability of Stopping Early	Sample Size Avg
0.10	0.017	11.9
0.20	0.099	11.4
0.30	0.254	10.5
0.40	0.462	9.2
0.50	0.650	8.1

- Operating Characteristics acquired using the Stata command stopbound

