If the true toxicity rate is 0.50, there is a 65.0% probability of stopping the trial early.

Descriptive statistics will be used to summarize the study data. For each study cohort, we will tabulate toxicities by dose, severity, and relationship to the treatment plan. The method of Kaplan and Meier will be used to estimate median PFS and OS.

A Toxicity/Efficacy Summary will be submitted to the IND Medical Monitor after the first 6 evaluable subjects per cohort, complete 4 months from the initiation of Radiation Therapy and prior to the enrollment of the next cohort, and following the treatment of the next 6 evaluable subjects to each cohort.

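### Does the toxicity stopping rule in Section 7.2 contradict itself about when it is applied?

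*Combined protocol and SAP*

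**What the plan says.** Section 7.2 gives a Bayesian rule with a beta(0.6, 1.4) prior: "If we determine there is more than a 80% chance that the treatment-related toxicity rate is more than 30%, we will stop the trial". That sentence names no number of evaluated patients. The sentence introducing the method calls the monitoring continuous and applies it "for each study cohort of 12 patients in cohorts of size 6". From criterion and prior the section derives the counts 3/6 and 6/12. It then explains that a cohort stops with 3 or more toxicities in the first 6 patients, "or if we observe 6 treatment related toxicities at any time while evaluating all 12 patients".

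Accrual is held after six patients to make sure that none of "the stopping boundaries have been reached prior to enrolling the final 6 patients of each study cohort". On performance it says: "The operating characteristics from this decision rule are shown in Table X and are based on 1000 simulations for each scenario", and then "If the true toxicity rate is 0.50, there is a 65.0% probability of stopping the trial early". Summaries go to the IND Medical Monitor "after the first 6 evaluable subjects per cohort, complete 4 months from the initiation of Radiation Therapy" and again "following the treatment of the next 6 evaluable subjects to each cohort".

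Two other places bear on the schedule. Section 4.1 plans a single pause for toxicity assessment, halfway through each arm. Section 4.4.1.2 (Management of Radiation Pneumonitis) repeats 3/6 and 6/12 and says that 0, 1 or 2 of 6 lets the study go on. It counts radiation pneumonitis only, so it is used here for the schedule alone.

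**The concern.** Three features suggest checks between the two looks: the word continuous, a criterion with no patient number, and the reference to any time. If the criterion were applied after each patient from the sixth on, it would demand a stop at counts where 3/6 and 6/12 do not. At 4 toxicities in 8 evaluated patients, for example, one reader could stop the cohort and another could wait for six.

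The rule guards the primary endpoint. If its timing were really open, the governing wording could be chosen after the toxicity data were seen. Table X would then describe only one of the possible rules.

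**Working it through.** **Inputs (Section 7.2).** Prior beta(0.6, 1.4); stop if Pr(rate > 0.30 | data) > 0.80; counts 3/6 and 6/12; 1000 simulations per row of Table X. Prior mean 0.6/2 = 0.30; SD = √(0.3 × 0.7/3) = 0.265. Both match the text.

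**1. Do the counts follow from the criterion at 6 and 12?** With x toxicities in n patients the posterior is Beta(0.6 + x, 1.4 + n − x). Its probability above 0.30 is:

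| x/n | Pr(rate > 0.30) | Criterion |
|---|---|---|
| 3/6 | 0.800003 | stop (just) |
| 5/12 | 0.772 | continue |
| 6/12 | 0.905 | stop |

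The criterion is therefore met at both printed counts, and 5/12 does not meet it. A count of 3 in 6 clears 0.80 only marginally, so 2 in 6 does not.

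**2. Which schedule does Table X describe?** The exact probability of stopping at the first look is P(X ≥ 3), X ~ Binomial(6, p). The either-boundary column comes from exact enumeration with looks at 6 and 12.

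| True rate | Table X, stop early | Exact, stop at 6 | Table X, average N | 12 − 6 × Table X probability | Exact, either boundary |
|---|---|---|---|---|---|
| 0.10 | 0.017 | 0.016 | 11.9 | 11.90 | 0.016 |
| 0.20 | 0.099 | 0.099 | 11.4 | 11.41 | 0.104 |
| 0.30 | 0.254 | 0.256 | 10.5 | 10.48 | 0.282 |
| 0.40 | 0.462 | 0.456 | 9.2 | 9.23 | 0.519 |
| 0.50 | 0.650 | 0.656 | 8.1 | 8.10 | 0.747 |

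The simulation standard error at rate 0.50 is √(0.650 × 0.350/1000) = 0.0151, so the difference is (0.656 − 0.650)/0.0151 = 0.4 SE. Every row lies within 0.5 SE. The average-N column equals 12 − 6 × the stopping probability throughout, so every early stop in the table falls at patient 6. Counting a stop at six toxicities anywhere before patient 12 would give 0.703 at rate 0.50, which is (0.703 − 0.650)/0.0151 = 3.5 SE away. Table X is the two-look rule.

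**3. What would between-look checks do?** Assume 4-month outcomes mature one by one in enrolment order, and apply the criterion after each patient from 7 on. After at most 2/6, the reachable first crossings are 4/8 (0.846), 5/10 (0.880) and 5/11 (0.829). Neither 4/9 (0.782) nor 4/10 (0.711) crosses.

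| True rate | Crosses between looks | Outcome differs from the counts | Overall stopping |
|---|---|---|---|
| 0.10 | 0.2% | 0.2% | 1.8% |
| 0.20 | 2.2% | 1.7% | 12.1% |
| 0.30 | 7.2% | 4.6% | 32.8% |
| 0.40 | 12.6% | 6.3% | 58.2% |
| 0.50 | 14.3% | 5.2% | 79.9% |

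The last column is the either-boundary figure plus the middle column; at rate 0.30, 28.2 + 4.6 = 32.8.

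**4. Is that schedule in the plan?** A literal patient-by-patient rule would start at patient 1. It would already be met at 2/2 (0.928), 2/3 (0.838) and 3/5 (0.875), and would stop 82.1% of cohorts at rate 0.50. No section describes that, nor a rule that becomes continuous only after patient 6.

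**5. Would earlier stopping spare patients?** Assume even accrual of each cohort over the 12–16 months in Section 1.0, radiation starting at enrolment, and the 4-month hold inside or on top of that period. At the slowest, 16 months over 10 gaps is 1.6 months per patient. In the 4 months until patient 8 is evaluable, 4/1.6 = 2.5, so two more enter and 10 of 12 are in. At faster rates up to all 12 are. When patient 10 is evaluable, all 12 are in. At most two enrolments would be saved.

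**The case for a change.** The best case for a change is that no sentence states outright the numbers of patients at which the rule applies. The reference to groups of six also appears earlier in Section 7.2 as a description of enrolment, so it need not describe the looks. Someone facing 4/8 or 5/11 could cite the criterion for stopping and the counts for continuing. Naming the looks would cost a line of text. The plan also does not report the chance of crossing either boundary, 74.7% at a true rate of 0.50.

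The between-look arithmetic stands, given its ordering assumption, and the wording is loose. The claim that the governing rule is open does not stand. Section 7.2 moves from criterion to counts as a consequence, and no place in the documents prints any other count. The hold at six, the single pause and the two reports all follow that schedule. The phrase about any time changes no outcome, because six toxicities among 12 or fewer patients already settle 6/12; removing it would only delay recognition. The 65.0% is correctly called early stopping, since a crossing at patient 12 stops nothing early. An either-boundary column would be useful to some readers, but its absence is not an error.

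**Conclusion.** No change follows. With the criterion evaluated at 6 and 12 patients per cohort, the criterion, the counts and Table X agree. An analyst reading Section 7.2 together with Sections 4.1 and 4.4.1.2 would apply it that way. Naming the looks explicitly would move no boundary, operating characteristic or sample size.

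The alternative would bring in a schedule the plan does not describe. It would raise stopping from 28.2% to 32.8% at a true rate of 30%, the tolerated limit, and from 10.4% to 12.1% at 20%, while saving at most two enrolments. That is a design choice, not the repair of an error.

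The agreement at 6 and 12 and the match to Table X rest only on the stated prior, threshold and counts. The between-look percentages also assume that outcomes mature in enrolment order. The enrolment figure assumes even accrual and radiation starting at enrolment.

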## 8.0 LABELING, PACKAGING, STORAGE AND RETURN OF CLINICAL SUPPLIES

### 8.1 Investigational Product

The investigator shall take responsibility for and shall take all steps to maintain appropriate records and ensure appropriate supply, storage, handling, distribution and usage of investigational product in accordance with the protocol and any applicable laws and regulations.

Clinical Supplies will be provided by Merck as summarized in Table 7.

Table 7 Product Descriptions

Product Name & Potency	Dosage Form
Pembrolizumab 50 mg	Lyophilized Powder for Injection
Pembrolizumab 100 mg/ 4mL	Solution for Injection

## **8.2 Packaging and Labeling Information**

Clinical supplies will be affixed with a clinical label in accordance with regulatory requirements.

## **8.3 Clinical Supplies Disclosure**

This trial is open-label; therefore, the subject, the trial site personnel, the Sponsor and/or designee are not blinded to treatment. Drug identity (name, strength) is included in the label text; random code/disclosure envelopes or lists are not provided.

## **8.4 Storage and Handling Requirements**

Clinical supplies must be stored in a secure, limited-access location under the storage conditions specified on the label.

Receipt and dispensing of trial medication must be recorded by an authorized person at the trial site.

Clinical supplies may not be used for any purpose other than that stated in the protocol.

## **8.5 Returns and Reconciliation**

The investigator is responsible for keeping accurate records of the clinical supplies received from Merck or designee, the amount dispensed to and returned by the subjects and the amount remaining at the conclusion of the trial.

Upon completion or termination of the study, all unused and/or partially used investigational product will be destroyed at the site per institutional policy. It is the Investigator's responsibility to arrange for disposal of all empty containers, provided that procedures for proper disposal have been established according to applicable federal, state, local and institutional guidelines and procedures.

## 9.0 APPENDICES

### 9.1 ECOG Performance Status

Grade	Description
0	Normal activity. Fully active, able to carry on all pre-disease performance without restriction.
1	Symptoms, but ambulatory. Restricted in physically strenuous activity, but ambulatory and able to carry out work of a light or sedentary nature (e.g., light housework, office work).
2	In bed <50% of the time. Ambulatory and capable of all self-care, but unable to carry out any work activities. Up and about more than 50% of waking hours.
3	In bed >50% of the time. Capable of only limited self-care, confined to bed or chair more than 50% of waking hours.
4	100% bedridden. Completely disabled. Cannot carry on any self-care. Totally confined to bed or chair.
5	Dead.

\* As published in Am. J. Clin. Oncol.: *Oken, M.M., Creech, R.H., Tormey, D.C., Horton, J., Davis, T.E., McFadden, E.T., Carbone, P.P.: Toxicity And Response Criteria Of The Eastern Cooperative Oncology Group. Am J Clin Oncol 5:649-655, 1982.* The Eastern Cooperative Oncology Group, Robert Comis M.D., Group Chair.

### 9.2 Common Terminology Criteria for Adverse Events V4.0 (CTCAE)

The descriptions and grading scales found in the revised NCI Common Terminology Criteria for Adverse Events (CTCAE) version 4.0 will be utilized for adverse event reporting. (<http://ctep.cancer.gov/reporting/ctc.html>)

### 9.3 Response Evaluation Criteria in Solid Tumors (RECIST) 1.1 Criteria for Evaluating Response in Solid Tumors

RECIST version 1.1\* will be used in this study for assessment of tumor response. While either CT or MRI may be utilized, as per RECIST 1.1, CT is the preferred imaging technique in this study.

\* As published in the European Journal of Cancer:

E.A. Eisenhauer, P. Therasse, J. Bogaerts, L.H. Schwartz, D. Sargent, R. Ford, J. Dancey, S. Arbuck, S. Gwyther, M. Mooney, L. Rubinstein, L. Shankar, L. Dodd, R. Kaplan,

D. Lacombe, J. Verweij. New response evaluation criteria in solid tumors: Revised RECIST guideline (version 1.1). *Eur J Cancer*. 2009 Jan;45(2):228-47.

## 9.4 Events of Clinical Interest Guidance Document

Document attached as Appendix G in PDOL system.

